9.2.2 Adverse Events of Special Interest for Upadacitinib

Adverse events of special interest will be summarized by SOC and PT and listing format and will be based on standard or company MedDRA queries (SMQs or CMQs) 1) from Baseline to Week 16 visit and 2) the entire treatment period, respectively.

Detailed information about the search criteria are provided in [Appendix B](#).

Tabular listings of selected adverse events of special interest will be provided.

9.2.3 Adverse Events of Other Safety Topics of Interest

Adverse Events of Other Safety Topics of Interest will be summarized by SOC and PT and listing format and will be based on standard or company MedDRA queries (SMQs or CMQs or selected PTs) 1) from Baseline to Week 16 visit and 2) the entire treatment period, respectively.

Detailed information about the search criteria are provided in [Appendix J](#).

Tabular listings of Adverse Events of Other Safety Topics of Interest will be provided.

9.3 Analysis of Laboratory Data

Analyses of selected laboratory data will be performed in safety population. Data collected from central and local laboratories, including additional laboratory testing due to an SAE, will be used in all analyses, except for Baseline derivation where SAE-triggered laboratory assessments on or before the first dose of study drug will be excluded.

For the analysis of laboratory data, values observed up to 30 days after the last dose of upadacitinib or 84 days after the last dose of dupilumab will be included.

All laboratory parameters to be collected in this study are listed below. Laboratory parameters will be reported using the standard international (SI) units. The selected clinical laboratory tests defined in the protocol operations manual (e.g., hematology and clinical chemistry) will be summarized.

Table 2. List of Laboratory Values

Clinical Laboratory Tests		
Hematology	Clinical Chemistry	Other Tests
Hematocrit	BUN	Central Lab Tests: Estimated glomerular filtration rate (eGFR)
Hemoglobin	Creatinine	International normalized ratio (INR)
RBC count	Total bilirubin	Serum pregnancy (beta human chorionic gonadotropin [bHCG]) test
WBC count	INR (reflex only) ^a	Hepatitis Screening:
Neutrophils	Albumin	Hepatitis B surface antigen (HBs Ag)
Bands	ALT	Hepatitis B surface antibody (HBs Ab)
Lymphocytes	AST	Hepatitis B core antibody (HBc Ab)
Monocytes	Alkaline phosphatase	Hepatitis B virus deoxyribonucleic acid polymerase chain reaction (HBV DNA PCR [rIreflex only])
Basophils	CPK	Hepatitis C virus antibody (HCV Ab)
Eosinophils	Sodium	Hepatitis C virus ribonucleic acid (HCV RNA [reflex only])
Platelet count	Potassium	Human immunodeficiency virus antibody (HIV Ab)
Urinalysis		
Specific gravity	Bicarbonate/CO ₂	QuantiFERON-TB Gold
Ketones	Chloride	High-sensitivity C-reactive protein (hsCRP)
pH	Calcium	Follicle stimulating hormone (FSH) ^b
Protein	Inorganic phosphorus	Drug and alcohol screen
Blood Glucose	Uric acid	Local Lab Tests:
Urobilinogen	Total protein	Urine pregnancy test
Bilirubin	Glucose	Varicella antibody, if indicated
Leukocytes	Cholesterol	PPD test / T-SPOT TB
Nitrites	LDL-C	
Microscopic examination, if needed	HDL-C	
	Triglycerides	

Ab = antibody; ALT = alanine aminotransferase; AST = aspartate aminotransferase; bHCG = beta human chorionic gonadotropin; BUN = blood urea nitrogen; CO₂ = carbon dioxide; CPK = creatine phosphokinase; DNA = deoxyribonucleic acid; FSH = follicle-stimulating hormone; HBc Ab = hepatitis B core antibody; HBs Ab = hepatitis B surface antibody; HBs Ag = hepatitis B surface antigen; HBV = hepatitis B virus; HCV Ab = hepatitis C virus antibody; HDL-C = high-density lipoprotein cholesterol; HIV = human immunodeficiency virus; hsCRP = high sensitivity C-reactive protein; INR = international normalized ratio; LDL-C = low-density lipoprotein cholesterol; PCR = polymerase chain reaction; RBC = red blood cell; RNA = ribonucleic acid; TB = tuberculosis; WBC = white blood cell

- INR will only be measured if ALT and/or AST > 3 × upper limit of normal (ULN).
- At screening only for female < 55 years old.

Analysis of Quantitative Laboratory Parameters (Hematology and Chemistry)

Analyses of selected hematology, chemistry, and urinalysis variables which are measured longitudinally will be performed by visits and by treatment groups. For analysis at each visit, the following summary statistics of visit values will be presented for each treatment group: sample size, mean, standard deviation, minimum, median, and maximum.

An ANOVA with treatment as a fixed factor will be used to present mean difference vs. dupilumab and associated 95% CIs for selected laboratory variables. Summaries for the Baseline and visit/final value means will be presented for subjects who have both Baseline and post-baseline values. Categorical data will be summarized using frequencies and percentages. If there are multiple post-baseline measurements on the same day, average value will be used.

Shift Table Analyses

Selected laboratory parameters will be tabulated using shift tables from Baseline to the worst value in each Period by NCI CTCAE. Selected lipid parameters will be summarized using National Cholesterol Education Program (NCEP) Adult Treatment Panel III (ATPIII) guidelines and details can be find in [Appendix D](#). A similar shift table will be provided to summarize shifts from Baseline to the final post-baseline value.

Percent Change from Baseline in Immunoglobulin E

Immunoglobulin E percent change from baseline will be provided by visit. A summary including number of subjects, min, 25% quartile, median, 75% quartile, and max will be provided by visit. No statistical modeling will be applied.

Potentially Clinically Important Laboratory Values

Laboratory abnormalities will be evaluated based on Potentially Clinically Important (PCI) criteria (NCI CTCAE criteria of Grade 3 or above) with a grade worsening compared to Baseline. For each laboratory PCI criterion, the number and percentage of

subjects who have a laboratory value meeting the criteria will be summarized. Listings will be provided to summarize subject-level laboratory data for subjects meeting PCI criteria. The PCI criteria are defined in [Appendix C](#) using CTCAE 4.03.

Liver Function Tests

According to FDA's Guidance for Industry "Drug-Induced Liver Injury: Premarketing clinical evaluation (July 2009), when aminotransferase (AT) abnormalities indicating hepatocellular injury are accompanied by evidence of impaired hepatic function (bilirubin elevation $> 2 \times$ ULN), in the absence of evidence of biliary obstruction (i.e., significant elevation of ALP) or some other explanation of the injury (e.g., viral hepatitis, alcohol hepatitis), the combined finding (i.e., Hy's Law cases) represents a signal of a potential for the drug to cause severe DILI. For the purpose of assessing for potential Hy's law cases, the frequencies and percentages of subjects with post-baseline liver specific function test values that meet the following criteria of potential clinical interest should be presented:

- ALT $\geq 3 \times$ ULN
- ALT $\geq 5 \times$ ULN
- ALT $\geq 10 \times$ ULN
- ALT $\geq 20 \times$ ULN
- AST $\geq 3 \times$ ULN
- AST $\geq 5 \times$ ULN
- AST $\geq 10 \times$ ULN
- AST $\geq 20 \times$ ULN
- TBL $\geq 2 \times$ ULN
- Alkaline phosphatase $\geq 1.5 \times$ ULN
- ALT and/or AST $\geq 3 \times$ ULN and concurrent TBL $\geq 1.5 \times$ ULN
- ALT and/or AST $\geq 3 \times$ ULN and concurrent TBL $\geq 2 \times$ ULN

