## 7.4 Statistical Analyses for Safety

---

The safety analyses will be carried out using the Safety Population and will be based on treatments the subjects actually received. Safety will be assessed by AEs, physical examination, laboratory assessments, and vital signs. Note that missing safety data will not be imputed. Analysis details will be specified in the SAP.

Adverse events will be coded using MedDRA. Treatment-emergent AEs (TEAEs) are defined as those that began or worsened in severity after the first dose of study drug and no more than 5 half-lives of the drug after the last dose of study drug. Specifically, 30 days will be used for upadacitinib, and 84 days (12 weeks) will be used for dupilumab. The number and percentage of subjects experiencing TEAEs will be tabulated using the MedDRA SOC and preferred term (PT), by severity, and by relationship to the study drug as assessed by the investigator. Summaries (including percentages and events per 100 patient-years) of SAEs, deaths, AEs leading to discontinuation and AESIs will be provided as well. Pre-treatment AEs will be summarized separately.

For laboratory and vital signs, mean change from Baseline and percentage of subject with evaluations meeting criteria for pre-defined Potentially Clinically Significant values will be summarized.

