8.1.1 Analysis of Efficacy Endpoints by Variable Type

Analysis of Categorical Variables

For ITT Population, frequencies and percentages will be summarized along with 95% confidence interval (CI) based on normal approximation. For ITT Population, pairwise comparisons of upadacitinib vs. dupilumab will be made using CMH test using stratification factor as baseline vIGA-AD categories (vIGA-AD 3 or 4). Point estimates, *p*-value, and 95% CIs for the difference in proportions between upadacitinib and dupilumab will be provided. Construction of CIs for the common risk difference will be based on the Mantel-Haenszel estimate adjusting for stratification factors. Breslow-Day test will be performed to test the homogeneity between strata.

NRI-C will be the primary approach for categorical endpoints (Section 8.2). In addition, the primary endpoint and all key secondary categorical endpoints will be analyzed using MI defined in Section 8.2 as the sensitivity approach. All categorical endpoints will be analyzed using NRI-NC defined in Section 8.2 as the sensitivity approach.

Analysis of Continuous Variables

For ITT Population, the Baseline and visit means will be presented for each treatment group who have both Baseline and post-baseline visit values. For ITT Population, Percent change from Baseline in the treatment groups will be compared using MMRM model as described in Table 1. Point estimates, SE, and 95% CIs of LS mean change from Baseline within treatment groups, and these statistics along with *p*-value between upadacitinib group and dupilumab will be provided.

Table 1. Model of Continuous Variables

Population	Model	Adjust for Stratification Factor(s)
ITT	MMRM model includes the categorical fixed effects of treatment, visit and treatment-by-visit interaction, and the continuous fixed covariates of Baseline measurement.	vIGA-AD categories at randomization

All efficacy endpoints will be analyzed overall and within each stratum of the stratification factors: baseline vIGA-AD categories and age group Analysis model within each stratum will not be adjusted for stratification factors.

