8.2.2 Continuous Endpoints

For continuous endpoints, missing data will be handled using Mixed-Effect Model Repeat Measurement (MMRM).

- The MMRM will be conducted using mixed model including observed measurements at all visits, except that measurements after any rescue medication will be excluded. The mixed model includes the fixed effects of categorical variable of treatment, visit and treatment-by-visit interaction, main stratification factor at randomization (baseline vIGA-AD categories), and the continuous variable of Baseline measurement. An unstructured variance covariance matrix (UN) will be used. If the model cannot converge, an appropriate covariance structure matrix (e.g., autoregressive (1) or compound symmetry) will be used. The parameter estimations are based on the method of restrictive maximum likelihood (REML). The fixed effects will be used to report model-based means at corresponding visits.

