9.4 Analysis of Vital Signs

Analyses of selected vital signs variables will be performed in the safety population. For each analysis, the following summary statistics will be presented by visit for each treatment group: sample size, mean, standard deviation, minimum, median, and maximum.

For the analysis of vital signs data, values observed up to 30 days after the last dose of upadacitinib or 84 days after the last dose of dupilumab will be included.

An ANOVA model with only treatment as a factor will be used to present confidence intervals for the difference between upadacitinib group and dupilumab group. Mean difference from dupilumab and associated 95% CIs will be presented. Summaries of the Baseline and visit/final value means will be presented for subjects who have both Baseline and post-baseline values.

If there are multiple post-baseline measurements on the same day, the average value will be used.

The vital signs variables will be evaluated based on the PCI criteria. For each vital signs PCI criterion, the number and percentage of subjects who have a vital sign value meeting the criteria at least once during the analysis period will be summarized. Listings will be provided to summarize subject-level vital sign data for subjects meeting PCI criteria. The PCI criteria are defined in [Appendix C](#).

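### The laboratory and vital-sign ANOVA names no response variable and omits the baseline value, so its descriptive intervals are valid but wider than they need to be

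*SAP*

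**What the plan says.** SAP 9.3 (laboratory data): "An ANOVA with treatment as a fixed factor will be used to present mean difference vs. dupilumab and associated 95% CIs". SAP 9.4 (vital signs) is more explicit about the model terms: "An ANOVA model with only treatment as a factor will be used to present confidence intervals for the difference", followed by "Mean difference from dupilumab and associated 95% CIs will be presented". Neither section says what the mean is a mean of.

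The surrounding text points two ways:

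- SAP 9.3 describes the by-visit tables in terms of observed values: "the following summary statistics of visit values will be presented for each treatment group". It adds "Summaries for the Baseline and visit/final value means will be presented for subjects who have both Baseline and post-baseline values". SAP 9.4 has a near-identical sentence.
- Protocol 7.4 promises a different quantity: "For laboratory and vital signs, mean change from Baseline and percentage of subject with evaluations meeting criteria" for pre-defined thresholds. It does not mention the ANOVA, and it leaves analysis details to the SAP.

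The efficacy model is fully specified by comparison. SAP 8.1.1 names percent change from Baseline as the response and includes baseline ("and the continuous fixed covariates of Baseline measurement"). SAP 8.2.2 repeats this ("and the continuous variable of Baseline measurement").

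**The concern.** There are two linked gaps.

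The first is the response. In the same subjects, the between-arm difference in visit values and the between-arm difference in changes differ by exactly the between-arm difference at baseline. Two programmers working from SAP 9.3 and 9.4 could therefore produce different estimates and intervals from one database.

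The second is the covariate. On the change reading, baseline enters by subtraction with a fixed coefficient of one. On the visit-value reading it does not enter at all. Neither is the most precise use of a value already collected, and both leave the estimate exposed to chance imbalance in that parameter.

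What is at stake is modest. Type I error control in SAP 11.0 covers only the primary and ranked secondary endpoints, and no decision rule rests on these intervals. Still, the study objective includes safety against dupilumab, Protocol 2.2 lists several laboratory changes seen with upadacitinib, and these ANOVAs are the only modelled between-arm comparison of laboratory and vital-sign means.

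**Working it through.** **The plan's own figures.** The documents give no precision figure for these contrasts, so there is none to reproduce. The one power statement (SAP 2.4: above 80% for 50% versus 62%, 325 per arm, two-sided 0.05) recomputes to 87.1% and is unaffected.

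**Inputs.** n = 325 per arm (SAP 2.4), used here as the size of each safety arm at a visit. SD = 1 at both times, so results are in SD units. The documents give no correlation ρ between baseline and follow-up; 0.5 to 0.8 is assumed.

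**Standard errors of the treatment difference.**

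- ANOVA on visit value: √(2/n) = √(2/325) = 0.0784
- ANOVA on change: √(4(1−ρ)/n)
- ANCOVA with baseline: √(2(1−ρ²)/n)

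The 95% half-width is 1.96 × SE.

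| ρ | SE visit | SE change | SE ANCOVA | SE cut vs change | SE cut vs visit |
|---|---|---|---|---|---|
| 0.5 | 0.0784 | 0.0784 | 0.0679 | 13.4% | 13.4% |
| 0.6 | 0.0784 | 0.0702 | 0.0628 | 10.6% | 20.0% |
| 0.7 | 0.0784 | 0.0608 | 0.0560 | 7.8% | 28.6% |
| 0.8 | 0.0784 | 0.0496 | 0.0471 | 5.1% | 40.0% |

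As ρ goes from 0.5 to 0.8, the half-widths are 0.154 throughout for visit values, 0.154 to 0.097 for change, and 0.133 to 0.092 for ANCOVA. Outside that range, the planned interval relative to ANCOVA is 1.24 (change) and 1.05 (visit value) times as wide at ρ = 0.3, and 1.03 and 2.29 times at ρ = 0.9.

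**Overall coverage.** Simulation of 20,000 trials per correlation gave 0.948 to 0.953 for all three analyses. Omitting baseline does not bias the interval over randomisations.

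**Chance imbalance.** The baseline difference D has SE 0.0784, so P(|D| ≥ 0.1 SD) = 2 × (1 − Φ(0.1/0.0784)) = 0.202 for any one parameter. Given D, the visit-value estimate is off by ρD on average and the change estimate by −(1−ρ)D, while ANCOVA is centred. Coverage in the randomisations with |D| ≥ 0.1 SD:

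| ρ | Change: exact (simulated) | Visit value: exact (simulated) | ANCOVA: simulated |
|---|---|---|---|
| 0.5 | 0.888 (0.876) | 0.888 (0.893) | 0.951 |
| 0.8 | 0.925 (0.932) | 0.798 (0.807) | 0.954 |

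Exact and simulated values agree to about one percentage point.

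The other 79.8% of randomisations cover above 95% to compensate. For change, (0.950 − 0.202 × 0.888)/0.798 = 0.966 at ρ = 0.5 and (0.950 − 0.202 × 0.925)/0.798 = 0.956 at ρ = 0.8. For visit values at ρ = 0.8, (0.950 − 0.202 × 0.798)/0.798 = 0.988.

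**Effect of the covariate on the ambiguity.** If y − b = α + τ·treatment + β·b, then y = α + τ·treatment + (β + 1)·b. The treatment effect τ and its interval are identical whether the response is change or visit value. Once baseline is in the model, the choice of response no longer alters the contrast.

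**The case against.** The best case for leaving the text alone is this. Protocol 7.4 names change from Baseline. SAP 1.0 says departures from the protocol are listed in Section 12.0, and that list drops nothing here. Reporting Baseline and visit means in paired subjects is the usual layout of a change table. Read together, the documents favour change, and on that reading the gain from ANCOVA is only 5% to 13%, or about 3% in width at ρ = 0.9. A treatment-only model is a legitimate choice for descriptive safety means. An efficacy MMRM for ranked endpoints need not dictate it. The 40% reduction and the coverage near 80% apply only to the less supported reading, and conditional coverage picks out the worst fifth of randomisations. Shift tables and most of the potentially-clinically-important criteria already use baseline without this model.

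Much of this stands. Change is the better-supported reading, the smaller gain goes with it, and no figure here implies an invalid interval. But the protocol sentence concerns a summary, not the model, and Protocol 7.4 leaves analysis details to the SAP, whose own wording concerns values. The covariate costs nothing, improves precision under either reading whenever ρ lies strictly between 0 and 1, and removes the dependence on chance imbalance.

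**Conclusion.** The point holds, as a low-impact improvement to consider. SAP 9.3 and 9.4 leave the ANOVA response unnamed and omit the baseline value, and nothing elsewhere supplies either for these models. On the reading that Protocol 7.4 supports, the standard error could be 13% to 5% smaller; on the visit-value reading, 13% to 40% smaller. These sizes assume ρ of 0.5 to 0.8, equal SDs at both times and 325 evaluable subjects per arm. Actual laboratory parameters will vary around them. At high correlation the missing response definition matters more than the missing covariate. The primary endpoint, sample size and type I error are not affected.

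**What to change.** In SAP 9.3 and 9.4:

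1. Name change from Baseline as the response, in line with Protocol 7.4.
2. Replace the treatment-only ANOVA with an ANCOVA containing treatment and the baseline value of the same parameter.
3. State that the model uses subjects with both a Baseline value and the post-baseline value concerned. This follows once change is the response, but the present text attaches the restriction only to the summary means.

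The cost is a few lines of SAP wording and one extra model term. No additional data are needed.

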9.4 Analysis of Vital Signs

Analyses of selected vital signs variables will be performed in the safety population. For each analysis, the following summary statistics will be presented by visit for each treatment group: sample size, mean, standard deviation, minimum, median, and maximum.

For the analysis of vital signs data, values observed up to 30 days after the last dose of upadacitinib or 84 days after the last dose of dupilumab will be included.

An ANOVA model with only treatment as a factor will be used to present confidence intervals for the difference between upadacitinib group and dupilumab group. Mean difference from dupilumab and associated 95% CIs will be presented. Summaries of the Baseline and visit/final value means will be presented for subjects who have both Baseline and post-baseline values.

If there are multiple post-baseline measurements on the same day, the average value will be used.

The vital signs variables will be evaluated based on the PCI criteria. For each vital signs PCI criterion, the number and percentage of subjects who have a vital sign value meeting the criteria at least once during the analysis period will be summarized. Listings will be provided to summarize subject-level vital sign data for subjects meeting PCI criteria. The PCI criteria are defined in [Appendix C](#).

10.0 Interim Analyses

There will be no efficacy or futility interim analyses.

10.1 Data Monitoring Committee

An external data monitoring committee (DMC) composed of persons independent of AbbVie and with relevant expertise in their field will review unblinded safety data from

the ongoing study. The primary responsibility of the DMC will be to protect the safety of the subjects participating in this study.

A separate DMC charter describes the roles and responsibilities of the DMC members, frequency of data reviews, relevant data to be assessed, and general operations.

Since there are no efficacy analyses for early stopping, no alpha adjustment is needed.

11.0 Overall Type-I Error Control

A multiple testing procedure will be used to provide strong control of the type 1 error rate at alpha = 0.05 (2-sided) across analyses comparing upadacitinib vs dupilumab with respect to the primary endpoint and ranked secondary endpoints. Specifically, testing will utilize a sequence of hypothesis testing for the primary endpoints followed by the ranked secondary endpoints, and will begin with testing the primary endpoints using α of 0.05 (2-sided) for upadacitinib vs dupilumab. If the primary endpoint achieves statistical significance, continued testing will follow a hierarchical order of the secondary endpoint. Only the significance of a higher ranked secondary endpoint implies the continuation of the next secondary endpoint.

Since there are no efficacy analyses for early stopping planned for the DMC review, no alpha spending is needed due to the DMC review.

